### **10.7.5.2 Other events to be reported**

#### **Pregnancy**

Pregnancy which occurs during a clinical trial must be reported to LEO Pharma A/S within one calendar day of first knowledge using the Pregnancy Follow-up Form supplied by LEO Pharma A/S. All pregnancies must be followed up until delivery or termination.

#### **Overdose**

Any overdose defined as any higher dose than prescribed for the individual subject must be reported on the adverse event form of the CRF book. AEs originating due to the overdose must be documented on a separate line.

#### **Aggravation of condition**

Any clinically significant aggravation/exacerbation/worsening of the initially treated condition compared to baseline, judged by an overall medical assessment, must be reported as an AE.

### **10.7.6 Serious adverse events**

#### **10.7.6.1 Reporting of Serious Adverse Events**

Any Serious Adverse Event (SAE), related or unrelated to the investigational product or any trial procedure after signature of the Informed Consent Form must be reported to LEO Pharma A/S on the (paper) **Serious Adverse Event Form – Clinical Trial** within **one calendar day, with the exception that:**

- After Week 20, non-related serious adverse events outside the treatment area should *not* be reported to LEO Pharma A/S (see [Table 2](#) and [Table 3](#))

---

An LSR classified as a SAE must be reported on the adverse event form in the CRF and reported to LEO Pharma A/S on the paper *Serious Adverse Event Form (SAE) – Clinical Trial*.

**Note:** Planned hospitalisation or planned prolonged hospitalisation do not fulfil the criteria for being an SAE. The elective nature of the event must be clearly documented in the subject's medical record.

SAEs must be reported on the adverse event form of the CRF book. Additionally reports must be made using the paper *Serious Adverse Event (SAE) Form – Clinical Trial*, supplied by LEO Pharma A/S. Apart from the assessment of the intensity, causal relationship to the investigational product(s) and/or trial procedures, the action taken and the outcome to date, this report must contain a comprehensive narrative description of the course of the event.

The completed LEO *Serious Adverse Event (SAE) Form – Clinical Trial* must be faxed or scanned and e-mailed Global Pharmacovigilance at LEO Pharma A/S:

LEO Pharma A/S Head Quarter  
Denmark, Global Pharmacovigilance  
[name]  
**Global Pharmacovigilance [contact]  
**E-mail:** [[contact]](mailto:[contact])

All other relevant reports of diagnostic procedures, hospital records, autopsy reports etc. must be included, as applicable or upon request from Global Pharmacovigilance.

The IRB(s)/IEC(s), regulatory authorities and concerned investigators will be notified of SAEs according to current regulation and local requirements.

All Suspected, Unexpected Serious Adverse Reactions (SUSARs) are subject to expedited reporting to regulatory authorities.

SAEs must be followed indefinitely until a final outcome has been established, i.e. the follow-up may continue beyond the end of the clinical trial.

### 10.7.7 Source Data

**Source data:** *All information in original records and certified copies of original records of clinical findings, observations, or other activities in a clinical trial necessary for the reconstruction and evaluation of the trial. Source data are contained in source documents (original records or certified copies). (ICH E6, 1.51).*

**Source documents:** *Original documents, data, and records (e.g., hospital records, clinical and office charts, laboratory notes, memoranda, subjects diaries or evaluation checklists, pharmacy dispensing records, recorded data from automated instruments, copies or transcriptions certified after verification as being accurate copies, microfiches, photographic negatives, microfilm or magnetic media, x-rays, subject files, and records kept at the pharmacy, at the laboratories and at medico-technical departments involved in the clinical trial). (ICH E6, 1.52).*

Source Data Verification (SDV) is a key function in assuring the sponsor that clinical trial information is recorded and handled in a way that allows its accurate reporting, interpretation and verification. Monitors will, during the conduct of the clinical trial, perform SDV to confirm the accuracy and completeness of CRFs by verifying selected (as specified below) data recorded in the CRF against data recorded in source documents to ensure such records are consistent.

To enable SDV, it is essential that what constitutes source data/documents (see definition above) for the clinical trial data to be collected in the CRF as well as where such data can be found at the trial site is established and agreed with the investigator at each trial site and documented prior to initiation of the clinical trial.

Source data cannot be entered directly into the CRF. Source data should as a general rule be recorded in the subject's medical record or other defined document normally used at the trial site. Source data may be entered on a worksheet only if the clinical trial requires capture of data, which are normally not part of the subject's medical record.

For this clinical trial, the following parameters collected in the CRF should be verifiable from source documents available at the trial site:

- 
- Date of trial visits and date leaving the clinical trial
  - Relevant medical history and diagnosis, including AK and other skin diseases
  - Nature of contraception used by the subject and result of pregnancy test(s), when applicable
  - Data for evaluation of eligibility criteria
  - Abbreviated physical examination
  - Dispensation/administration of trial medication and compliance
  - Concomitant medication (including changes) and diagnoses
  - Subject demographics (e.g. sex, date of birth)
  - Adverse events, (nature, dates)
  - LSRs and AK lesion count
  - Dates and reason for any biopsy
  - Biopsy results

In addition to the above, the following should be added to the subject's medical record in chronological order, i.e. when these are allocated to the subject:

- Date(s) of conducting the informed consent process including date of provision of subject information
- Date of enrolment
- CRF book number
- Study medication kit number(s)
- The fact that the subject is participating in a clinical trial in AK including treatment with ingenol mebutate gel, 0.015% or imiquimod cream, 5% for 36 months

## 10.8 EFFICACY EVALUATION

Evaluation of efficacy is a secondary objective.

### 10.8.1 Secondary Efficacy Response Criteria

The secondary response criteria are:

- Complete clearance after the last treatment cycle (at Week 8 or 16)
- Partial (at least 75%) clearance after the last treatment cycle (at Week 8 or 16)
- Complete clearance at 12 months, defined as no AKs at any time in the selected treatment area at any time from the last treatment cycle at Week 8 or 16 through to Month 12.

## **10.9 SAFETY EVALUATION**

The evaluation of the risk of SCC is the primary objective of this trial.

### **10.9.1 Primary Response Criterion**

Diagnosis of SCC (defined as invasive SCC i.e. excludes SCC in situ) in the treatment field across the 3-year trial period

### **10.9.2 Secondary Safety Response Criterion**

Diagnosis of SCC and other neoplasia in the treatment field over a 3-year period.

### **10.9.3 Safety Evaluation**

- Incidence and severity of LSRs
- Incidence of AEs
- Incidence of SAEs

### **10.9.4 Evaluation of (Serious) Adverse Events**

Any (serious) adverse events reported.

### **10.9.5 Evaluation of Laboratory Data**

Not applicable

## **10.10 STATISTICAL ANALYSIS**

All hypotheses will be tested using two-sided tests with a significance level of 0.05. The null hypothesis for all treatment arm comparisons is that there is no difference between the arms versus the two-sided alternative that there is a difference between the treatment arms.

Study results will be summarised into tabulations, listings and figures where appropriate.

### **10.10.1 Subject Qualification for Analysis**

All subjects for whom a signed informed consent is obtained and a CRF is started will be accounted for in the study report.

Efficacy analyses will be based on the Full Analysis Set (FAS), which is defined as all randomized subjects. Safety analyses will be based on the Safety Analysis Set, which is defined as all subjects who receive an initial study treatment and have safety data available.

---

A per protocol (PP) analysis set will be used as safety and efficacy subsets and will be defined as subjects in the FAS who complete the trial without major protocol deviations. The composition of the PP analysis set will be determined and documented in reviews of the study database. The safety and efficacy analyses based on the PP analysis set will be performed to support the results obtained for the primary and secondary safety and efficacy endpoints.

### **10.10.2 Subjects Disposition**

Frequencies of the analysis sets, in total and by treatment arm, will be tabulated. Also reasons for premature discontinuations from treatment and from the trial will be presented for the FAS.

### **10.10.3 Baseline Characteristics**

Descriptive statistics of demographic and other baseline characteristics will be presented for the FAS. Demographics will include age, sex, race, ethnic origin and skin types. Other baseline characteristics will include height, weight, vital signs, body temperature, other diagnoses and concomitant medication. Baseline AK characteristics will include treatment location (face or scalp) and baseline lesion count.

Categorical data will be summarized using the number and percentage of subjects in each category and treatment arm. Continuous data will be summarized using the mean, median, standard deviation (SD), minimum and maximum values.

### **10.10.4 Analysis of Efficacy**

#### **Analysis of Secondary Efficacy Endpoints**

The secondary efficacy endpoints are listed in section [10.8.1](#).

The complete and partial clearance rates after the last treatment cycle as well as the complete clearance rates at 12 months will be compared between the two treatment arms using a Cochran–Mantel–Haenszel stratified by country, anatomical location and history of SCC. The ratio of rates will be estimated together with its 95% confidence interval.

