#### AK lesion count

Recording of the number of clinically visible AK lesions identified in the selected treatment area on Day 1, Weeks 8, 16 (if retreated), and 20, and Months 12, 18, 24, 30 and 36.

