### Actinic keratosis

Lesions clinically atypical for AK or suspicious for malignancy should be biopsied to determine appropriate treatment.

Imiquimod has not been evaluated for the treatment of actinic keratoses on the eyelids, the inside of the nostrils or ears, or the lip area inside the vermilion border.

There are very limited data available on the use of imiquimod for the treatment of actinic keratoses in anatomical locations other than the face and scalp. The available data on actinic keratosis on the forearms and hands do not support efficacy in this indication and therefore such use is not recommended.

Imiquimod is not recommended for the treatment of AK lesions with marked hyperkeratosis or hypertrophy as seen in cutaneous horns.

During therapy and until healed, affected skin is likely to appear noticeably different from normal skin. Local skin reactions are common but these reactions generally decrease in intensity during therapy or resolve after cessation of imiquimod cream therapy. There is an association between the complete clearance rate and the intensity of local skin reactions (e.g. erythema). These local skin reactions may be related to the stimulation of local immune response. If required by the patient's discomfort or the intensity of the local skin reaction, a rest period of several days may be taken. Treatment with imiquimod cream can be resumed after the skin reaction has moderated.

Each treatment period should not be extended beyond 4 weeks due to missed doses or rest periods.

The clinical outcome of therapy can be determined after regeneration of the treated skin, approximately 4-8 weeks after the end of treatment.

No clinical experience exists with the use of imiquimod cream in immunocompromised patients.

No data are available on re-treating actinic keratoses that have cleared after one or two courses of treatment and subsequently recur, and any such use is therefore not recommended.

Data from an open-label clinical trial suggest that subjects with more than 8 AK lesions showed a decreased rate of complete clearance compared to patients with less than 8 lesions.

The skin surface area treated should be protected from solar exposure.

[Go to top of the page](#)

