7.4.1 Efficacy Criteria

The efficacy criteria as defined in the CCTP are the following secondary criteria

- Complete AK clearance after the last treatment cycle (at Week 8 or 16)
- Partial (at least 75%) AK clearance after the last treatment cycle (at Week 8 or 16)
- Complete AK clearance at 12 months, defined as no AKs in the selected treatment area at any time from the last treatment cycle at Week 8 or 16 through to Month 12.

The criteria will be analysed as described in the CCTP.

Complete and partial clearance will be summarised by visit with 95% CI of clearance percentage.

Percent reduction in AK count will be summarised by visit.

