Cleared	xxx	(xx.x)	xxx	(xx.x)
Not cleared	xxx	(xx.x)	xxx	(xx.x)
Total	xxx	(xxx.x)	xxx	(xxx.x)
Lower 95% CL ⁵ (Cleared)		(xx.x)		(xx.x)
Upper 95% CL ⁵ (Cleared)		(xx.x)		(xx.x)
Ratio of clearance rates ⁶			xx.xx	
95% CI ⁷			xx.xx to xx.xx	
p-value			x.xxx	

- 1) Partial clearance: At least 75% reduction in AK count
- 2) N: Number of subjects
- 3) Last treatment cycle is at Week 8 or Week 16
- 4) Subjects who were not clear at week 8 and by mistake not entered second treatment cycle are excluded
- 5) CL: Confidence limit
- 6) Cochran-Mantel-Haenszel estimate stratified by country, anatomical location and history of SCC
- 7) CI: Confidence interval

Signature Page for TMF-000141169 v1.0

Reason for signing: Approved	Manager Verdict(s) Name: PPD Capacity: Date of signature: 28-Aug-2019 12:29:26 GMT+0000
------------------------------	---

Reason for signing: Approved	Manager(s) Name: PPD Capacity: Date of signature: 28-Aug-2019 13:47:29 GMT+0000
------------------------------	---

Reason for signing: Approved	QC App Name: PPD Capacity: Date of signature: 30-Aug-2019 07:57:28 GMT+0000
------------------------------	---

Electronic signatures made within eTMF LEO are considered to be a legally binding equivalent of traditional handwritten signatures.

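### The clearance comparisons are valid as planned, but leave out the Day 1 AK count; adjusting for it in a pre-specified model would give a modest gain in precision at almost no cost

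*Protocol*

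**What the plan says.** Protocol 10.10.4 applies one method to the three clearance endpoints: a CMH comparison "stratified by country, anatomical location and history of SCC. The ratio of rates will be estimated together with its 95% confidence interval". SAP 7.4.1 adds no covariate: "The criteria will be analysed as described in the CCTP". Footnote 6 to Shell 12 in SAP Appendix II describes the reported ratio as a "Cochran-Mantel-Haenszel estimate stratified by country, anatomical location and history of SCC".

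The lesion count is collected. The synopsis provides for "Recording of the number of clinically visible AK lesions identified in the selected treatment area on Day 1, Weeks 8, 16 (if retreated), and 20", with further counts to Month 36. Its only baseline use is descriptive. Protocol 10.10.3 says "Baseline AK characteristics will include treatment location (face or scalp) and baseline lesion count", and SAP 7.1.2 does the same. Protocol 10.6.7 and 10.10.5 do not list it among the randomisation strata.

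Entry requires 5 to 9 lesions (Protocol 10.4.1). Complete clearance is a count of zero (Protocol 10.1.3, Visit 6). Partial clearance is a reduction of at least 75% (Shell 12, footnote 1). The imiquimod label in Protocol Appendix V, section 4.4, reports that "subjects with more than 8 AK lesions showed a decreased rate of complete clearance compared to patients with less than 8 lesions".

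**The concern.** A subject with nine lesions must lose nine to count as completely cleared; a subject with five must lose five. Unless each lesion responds better when there are more of them, the count should predict the outcome. A baseline value that predicts the outcome, and that neither randomisation nor analysis uses, leaves explainable variation in the error term.

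Partial clearance also depends on the count, because a percentage cut-off acts on small whole numbers: one lesion may remain at counts 5 to 7, two at counts 8 and 9.

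Protocol 10.10.6.1 rules out a formal test for the SCC endpoints, so the clearance comparisons are the trial's only formally tested between-arm comparisons. At stake is the width of the interval for the ratio of rates, and some protection against choosing an adjustment after the fact if counts happen to differ between arms.

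**Working it through.** **Inputs from the documents.** 480 subjects, 240 per arm (Protocol 10.3); counts 5 to 9; three countries, two locations, two SCC-history levels; two-sided 0.05 (Protocol 10.10).

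**Assumptions, not in the documents.** Counts uniform on 5-9; 85% clearance per lesion, independent (lesion-level model); or overall complete clearance of 55% with an odds ratio (OR) per extra lesion between 1.0 and 0.6. Simulations also assume 40% scalp, 20% with SCC history, blocks of 4, and countries in proportion to planned sites (17:15:16).

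**1. The plan's own figure.** The only design calculation concerns SCC. The upper limit p + 1.96 × √(p(1−p)/240) gives 2.26% at p = 1.0% and 4.48% at p = 2.5%, as stated. There is no design calculation for clearance.

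**2. Effect of the count under the lesion-level model.** Complete clearance is 0.85^n. Partial clearance is P(remaining ≤ k), with remaining ~ Binomial(n, 0.15) and k = floor(0.25n).

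| Day 1 count n | 5 | 6 | 7 | 8 | 9 |
|---|---|---|---|---|---|
| Complete | 44.4% | 37.7% | 32.1% | 27.2% | 23.2% |
| Lesions allowed to remain, k | 1 | 1 | 1 | 2 | 2 |
| Partial | 83.5% | 77.6% | 71.7% | 89.5% | 85.9% |

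Share of outcome variance explained, R² = Var(E[Y given n]) / (p̄(1−p̄)):
- Complete: p̄ = 0.329, so R² = 0.0056/0.2208 = 2.6%.
- Partial: p̄ = 0.816, so R² = 0.0040/0.1499 = 2.7%. The drop from 5 to 7 and the jump at 8 come from the cut-off; a straight line in n would miss them.

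Simulated variance ratios for complete clearance under lesion-level models were 0.97 to 0.99, a gain of 1-3%.

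**3. Model adjustment under a log-odds slope.** Standardised logistic log ratio of rates, without and with a linear count; 4,000 runs per row; 55% clearance. Percentage changes use unrounded SDs.

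| OR per lesion | SD without | SD with | SD change | Variance saved |
|---|---|---|---|---|
| 1.0 | 0.0831 | 0.0833 | +0.3% | none |
| 0.9 | 0.0831 | 0.0830 | −0.2% | 0.4% |
| 0.8 | 0.0835 | 0.0823 | −1.4% | 3% |
| 0.7 | 0.0830 | 0.0800 | −3.6% | 7% |
| 0.6 | 0.0842 | 0.0795 | −5.5% | 11% |

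The analytic R² at 55% agrees: 2.4%, 5.9% and 11.3% at OR 0.8, 0.7 and 0.6. Using 480 × R²/(1−R²), OR 0.8 is worth about 12 subjects and OR 0.6 about 61. Illustrative power for 55% v 44% is 67.5% with 240 per arm, 68.5% with 2.5% more effective subjects (about OR 0.8) and 70.1% with 6.3% more (about OR 0.7).

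**4. Validity of the planned CMH.** In null simulations (3,000 runs per scenario) the mean log ratio was within 0.003 of zero and type I error was 4.4% to 4.7%. The chance difference in mean count between arms has SD 1.41 × √(2/240) = 0.13 lesions. Adding the count moves the log ratio with SD 0.013 (OR 0.8) to 0.028 (OR 0.6), against a standard error of about 0.083.

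**5. The count as extra CMH strata.** The plan has 3 × 2 × 2 = 12 cells. Crossing in five counts gives 60 cells, an average of 480/60 = 8 subjects each, with about 17 subjects in one-arm cells that contribute nothing.

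| OR per lesion | 12 cells | 36 cells | 60 cells |
|---|---|---|---|
| 1.0 | 0.0811 | 0.0837 | 0.0869 |
| 0.8 | 0.0818 | 0.0827 | 0.0849 |
| 0.7 | 0.0825 | 0.0814 | 0.0839 |

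Entries are SDs of the log ratio under no treatment difference. Sixty cells are worse than twelve in every row, so the gain needs a model.

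**The case against.** The best defence is that analysing by the randomisation strata is a standard and valid choice, that these endpoints are secondary, that the sample size was set for SCC precision, and that a gain of perhaps 1% in the standard error is a matter of preference. All of that stands, and it limits this point to an optional refinement.

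Three stronger readings are tempting, and the documents do not support them.

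- A reader might infer that Appendix V establishes the count as a strong predictor. The label sentence opens "Data from an open-label clinical trial suggest that subjects with more than 8 AK lesions". It is tentative, gives no size, and concerns imiquimod and complete clearance only. With entry at 5 to 9, its higher group is just the subjects with nine lesions, and those with eight fall in neither group. The expectation rests mainly on the arithmetic of reaching zero.
- A reader might infer that chance imbalance in the count biases the reported ratio. It does not: under randomisation it is random error that the interval already covers (step 4). Adjustment removes part of that error; it corrects no bias.
- A reader might infer that the plan disregards the count altogether for partial clearance. The endpoint is a percentage reduction, so the count enters its definition. That is not adjustment, as the uneven row in step 2 shows.

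Timing also matters. The SAP is dated 28 August 2019, after the planned completion of the last subject in Q2 2018, and the trial is open label. A change of main estimator at that stage could be criticised as post hoc. This bears on how the model is introduced, not on whether it is more precise.

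**Conclusion.** The point holds as a modest, nearly free improvement in precision. None of the three clearance comparisons adjusts for a baseline count that the trial already collects and that is expected to affect clearance. The planned CMH is valid without it.

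The expected gain is about 1-3% of variance under lesion-level models and roughly 3-11% at odds ratios of 0.8 to 0.6 per lesion; that range is assumed. There is essentially no loss if the count is not prognostic. For partial clearance the only support is the R² of 2.7% under the 85% per-lesion assumption; no gain was simulated for that endpoint or for 12-month clearance. The primary SCC analysis is unaffected.

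**What to change.** In Protocol 10.10.4, SAP 7.4.1 and Shell 12:

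- Estimate the ratio of clearance rates from a logistic regression with treatment, country, anatomical location, history of SCC and Day 1 AK count, standardised over all subjects in the analysis, with a 95% CI.
- Enter the count as linear for the two complete-clearance endpoints, and as a factor for partial clearance because of the step between 7 and 8.
- State how the interval is computed (delta method or bootstrap) and which p-value is reported. A test of the standardised log ratio would agree with the interval.
- Keep the planned CMH ratio as supportive, with its 12 strata. Do not cross the count into them.
- Make the change before clearance results are examined by arm. If that is no longer possible, leave the CMH as the main result and label the model as an additional analysis.

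The cost is SAP wording, one covariate already in the database, and one extra model beside the CMH result for each endpoint and analysis set. No new data, visits or subjects are needed.
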